## Detailed Description of the Technology

The loop-mediated isothermal amplification (LAMP) assay has proven to be a reliable and simple protocol that can detect small amounts of viral RNA in patient samples. This LAMP protocol has the benefits of being simple, requiring no specialized equipment; rapid, requiring less than an hour from sample collection to readout; and cheap, costing around \$1 per reaction using commercial reagents. Heating to separate the reaction inhibitors from inactivated samples was shown to be an effective way to ensure reliable LAMP amplification. In this protocol, we take advantage of an open hardware solution invented by one of the PIs (SnapDx) that can be assembled with readily available components for the cost of <\$5 dollars a unit and could be used together with the LAMP assay for point of care detection of COVID-19 RNA from saliva. We further utilize a novel substrate - cellulose - for RNA extraction to further simplify the protocol for LAMP. Finally, we utilize a novel approach in construction of the assay to run the

home tests in a manner to eliminate any chances for reaction cross-contamination; common in laboratory molecular tests.

## **Instruments used with the Test:**

The SnapDx is designed to be a low-cost at-home device for detecting SARS-CoV-2 in saliva samples. The process utilizes LAMP (isothermal amplification) reagents to detect SARS-CoV-2 in saliva. With COVID-19 cases increasing globally, diagnostics need to be accessible to everyone, including resource-limited regions.

SnapDx test hardware: \$3-5 dollars per unit (estimate)

Saliva tube and solutions: \$1 dollar per unit (estimate)

## **Reagents and Materials:**

*Cost breakdown for reagents:*

- TCEP - 1G (Pierce 20490) >3000 reactions - \$80
- EDTA - 100mL (Sigma 03690) >10,000 reactions - \$40
- Primers - (IDT) 1.2ml of 10X >500 reactions - \$30
- NEB master mix (E1700L) >500 reactions - \$650

**Primers:** It is good practice to make 20 $\mu$ L 100 $\mu$ M aliquots once they are resuspended. In case of contamination a fresh stock can be used. For a 10X stock- 16  $\mu$ l FIP, 16  $\mu$ l BIP, 2  $\mu$ l F3, 2  $\mu$ l B3, 4  $\mu$ l LF, 4  $\mu$ l LB, and brought to 100  $\mu$ l with water.

Ordered from IDT, sequences from Rabe 2020.

As1\_F3

CGGTGGACAAATTGTCAC

As1\_B3

CTTCTCTGGATTAAACACACTT

As1\_LF

TTACAAGCTTAAAGAATGTCTAACACT

As1\_LB

TTGAATTTAGGTGAAACATTGTCACG

As1e\_FIP

TCAGCACACAAAGCCAAAATTATTTCTGTCAAAGGAAATTAAGGAG

As1e\_BIP

TATTGGTGGAGCTAAACTAAAGCCTTCTGTACAATCCCTTGAGTG

[figure not shown]
**Materials included in SnapDx Kit:**

Item	Manufacturer	Order Number
Spit tube	BIC	
SnapDx	BIC	
Instructions for Use	[name]	

**Materials included in the COVID-19 LAMP diagnostic assay (Gold Standard - clinically indicated):**

**Same as above.**

Item	Manufacturer	Order Number
LAMP master mix	NEB	M1804
primers	IDT	Standard Desalting

## Study Design

**Figure 1**

Study flowchart for recruitment, assay performance, and follow-up. Blue and yellow icons indicate processes and data collection respectively, in which key steps are colored with darker shades. CRC = Clinical Research Coordinator, PRO = patient reported outcome, MRN = medical record number.

## Usability/Feasibility

All study procedures involving contact with individuals of any infectious disease risk status (low, moderate, high) will be performed by trained clinical research personnel with all the necessary personal protective equipment. All of these personnel have also been vaccinated against COVID-19. Nonetheless they will use standard precautions, including getting tested weekly and staying away from others including study personnel and potential participants, in any case of symptoms or illness.

A cohort of 120 participants with diverse demographic backgrounds will be recruited and each of them will take one SnapDx test at our study site. Additional saliva samples will be collected to be used for laboratory testing for clinical evaluation purposes. Participants will complete a Usability Survey towards the end of taking the SnapDx on our study site to answer questions on satisfaction, ease, information, and use. These Usability questions include the following with multiple choice answers (strongly disagree, disagree, somewhat disagree, neither agree nor disagree, somewhat agree, agree, strongly agree):

- (Satisfaction) Overall, I am satisfied with how easy it was to use the test.
- (Ease) It was easy to learn to use this test.
- (Information) It was easy to find the information I needed.
- (Use) If the SnapDx test were available to me today, I would use this on a regular basis.
- We also ask If they would be willing to retake the test

Answers to these questions will be summarized and reported to the FDA as the results of our Human Usability Study.

## Validity

Saliva samples are to be collected in several patient populations, including from both inpatient and outpatient clinics, and COVID positive or negative patients determined by nasal swab PCR tests from several different locations. We will make a concerted effort to reach out to the Stanford and bay area communities and collect positive saliva samples from those who have tested positive through a standard PCR test. Five intended users will be given basic training to conduct SnapDx tests on these saliva samples as if they were taking the test themselves. A small portion of each saliva sample will also be tested for SARS-CoV-2 using saliva direct PCR in the laboratory. SnapDx test results will be compared against saliva direct PCR results to determine the positive percent agreement (PPA) and negative percent agreement (NPA).

## Aims

The aim of the study is to demonstrate the feasibility and validity of a saliva based home surveillance monitoring test for SARS-CoV-2 infection. These will be addressed in the following sub-aims.

- 1) To assess whether there is sufficient concordance between the technician and patient in interpretation of findings (Primary Feasibility Aim)
- 2) To assess sensitivity and specificity of the home saliva test (Primary Validity Aim)

### **Primary Feasibility Outcome:**

An indicator for discrepancy in interpretation of findings by participant versus by technician via photo (interrater reliability)

### **Secondary Feasibility Outcomes:**

There are 4 secondary outcomes involved in assessing feasibility. These include

- 1) An indicator for ambiguous findings as measured by percent confidence (if < 80% confident) in interpretation of results by participant and by technician (ease of interpretation)
- 2) An indicator that the participant appropriately followed instructions for using the kit ( $\geq 80\%$  confident) (ease of use)
- 3) An indicator for whether participant called technical support and by reason (e.g., device leaked or there was a possible broken part) (ease of use)
- 4) An indicator by participant that the sample was sufficient and reached the indicated line for sample integrity (sample integrity)

**Primary Validity Outcome:**

An indicator for whether the home saliva test is positive (to assess sensitivity and specificity)

**Statistical Considerations:****General Considerations:**

We will use the Agresti-Coull method (Agresti and Coull 1998) to construct confidence intervals. Unless otherwise noted, all confidence intervals constructed will be 95% confidence intervals.

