## Study Design Summary

Study Type:	Experimental
Estimated Enrollment:	3060 participants
Observational Model:	Cohort
Time Perspective:	Prospective
Official Title:	
Estimated Study Start Date:	September 2020
Estimated Primary Completion Date:	December 2021
Estimated Study Completion Date:	January 2022

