## Study Population:

The study population consists of a diverse group of Stanford faculty, staff, and students, and the local Santa Clara County community and specific external sources with known positive saliva samples and DUA/MTA in place. More specifically, there are three sub-populations to address our aims:

- 1) (Positive population) Hospitalized patients (N=15)
- 2) (High risk and positive population) People from Bay area community and external sites with known positive saliva samples and DUA/MTA in place; Those with a suspected COVID infection seeking testing within the Stanford Health Care system (N=1500)
- 3) (Low risk population) People from Bay area community; Students on the Stanford campus and employees at Stanford Health Care (N=1500)

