### **Analysis of the Validity Outcomes**

The sensitivity, specificity, positive predictive value (PPV), and negative predictive value (NPV) of the test will be estimated using the results collected in outpatients. The results of the PCR-based test will be the gold standard used to estimate the test's diagnostic accuracy. Home test results will only be included in this analysis if the test is performed within 24 hours of the time the swab used in the PCR tests was collected.

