### **Handling of Missing Data**

Although we have designed our study to minimize the amount of missing data, we expect to have a small amount of missing data. For example, hospitalized patients who are very sick or are discharged prior to day 5 may not provide data for days 1-5; participants may not complete the surveys each time they provide results from their home tests; or some PCR test results may not be able to be linked to the home test results. Analyses in the outpatient population will assume that data is missing at random and will use multiple imputation methods to account for the missing data. Given the small number of hospitalized patients expected, we will perform a complete case analysis in the analysis set consisting of hospitalized patients. Sensitivity analyses will be performed to evaluate the robustness of our findings to assumptions about missing data.

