### **Recruitment:**

The study will recruit up to 3060 participants including 60 hospitalized patients from multiple locations. These will include SHC COVID testing sites, Stanford Health Care

300 and 500P locations (the Emergency Department and other in-patient wards particularly M7, the COVID ward), as well as the front entrance of Stanford hospital and several locations on Campus. We will also be recruiting folks from the bay area community for our study. Participants will fall into two categories: i) those receiving a CLIA certified nasal swab COVID-19 test at SHC at the moment of recruitment, and ii) those not.

We will be recruiting a high-risk population because we will be recruiting from a pool that includes people who are seeking medical attention and/or participating in COVID-related research studies. Feasibility and validity of the tests will be evaluated in the high-risk population. We will be additionally recruiting a low-risk population to assess feasibility in the general population. Hospitalized patients will provide information on concordance between the CLIA COVID test and the home saliva test in patients over a five day period when we expect to see a mix of positive and negative tests.

To increase the number of SARS-CoV-2 positive saliva samples, we will accept deidentified and deactivated saliva samples from external sources, including Guatemala. All of these external sources will have DUA/MTA in place and will have institutional approval and have received written informed consent from all participants for the local trials, including the sharing of these samples with Stanford University for the current trial.

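### The hospitalised sample size is 15 in one section and 60 in another; a minor companion gap is that the only named interval makes no provision for repeat tests on one person

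*Combined protocol and SAP*

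**What the plan says.** **Hospitalised number.** Study Population lists three groups: "Positive population) Hospitalized patients (N=15", then 1500 high-risk or positive people and 1500 low-risk people. Recruitment states: "The study will recruit up to 3060 participants including 60 hospitalized patients from multiple locations". The Study Design Summary gives the estimated enrolment as "3060 participants".

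**Intervals.** General Considerations states "We will use the Agresti-Coull method", at the 95% level. No other interval method is named. No section mentions within-person correlation, a per-person summary, or selection of one test per person.

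**What is counted.** Analysis of the Feasibility Outcomes defines agreement with PCR as agreeing tests over all tests, in outpatients only. Consent and Test Protocol provide a bag that may hold more than one test, probably one or two, to be used on successive days. Handling of Missing Data expects that "participants may not complete the surveys each time they provide results from their home tests". The 120-person cohort under Usability/Feasibility takes a single test each.

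**Pairing with PCR.** Analysis of the Validity Outcomes is also confined to outpatients and adds: "Home test results will only be included in this analysis if the test is performed within 24 hours" of the swab. Data Acquired lists the chart review and the technician image readings only for people with a CLIA test inside the same window.

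**Hospitalised set.** Analysis Sets makes it one of two key sets, with a test a day over five days. Recruitment gives its purpose: "Hospitalized patients will provide information on concordance between the CLIA COVID test and the home saliva test in patients over a five day period". Handling of Missing Data specifies a complete-case analysis for it. Separately, the Validity section defines positive and negative percent agreement against saliva direct PCR on samples "including from both inpatient and outpatient clinics".

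**The concern.** A stated sample size should have one value. Here two sections of current text differ fourfold for the same group, and the groups in Study Population do not add to the enrolment stated elsewhere. Anyone judging how precisely the hospitalised results can be estimated gets an answer that depends on which section they read.

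The companion point is about the interval. Agresti-Coull is a single-proportion method that assumes independent trials. If one person gives two or more tests and the results are correlated within person, the nominal 95% interval is too narrow. The hospitalised concordance is where this could matter most. It has up to five tests per patient, and no formula or unit (test, day or patient) is given for it, because the written agreement and accuracy formulas are for outpatients.

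**Working it through.** **1. Totals.** The stated total is 3060.
- With the Recruitment figure: 60 + 1500 + 1500 = 3060, reproduced exactly.
- With the Study Population figure: 15 + 1500 + 1500 = 3015, short by 45 (45/3060 = 1.5%).
- The hospitalised group itself differs by 60/15 = 4.

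**2. Precision at the two sizes.** Agresti-Coull with z = 1.96: ñ = n + z², p̃ = (np + z²/2)/ñ, limits p̃ ± z√(p̃(1−p̃)/ñ). Take one test per patient and 80% agreement, which is the plan's own outpatient threshold used here as an illustration.
- n = 15: ñ = 18.84, p̃ = (12 + 1.92)/18.84 = 0.739, half-width 0.198, so 54.0–93.7%.
- n = 60: ñ = 63.84, p̃ = (48 + 1.92)/63.84 = 0.782, half-width 0.101, so 68.1–88.3%.
- The width ratio is about 0.198/0.101 = 2.0.
- If a third of patients have left by day 5 (assumed), the intervals are 47.9–95.4% (10 patients) and 65.0–89.8% (40 patients).

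**3. Repeat tests in outpatients.** The documents give no intraclass correlation (ICC); 0.5 is assumed, with a range of 0.1 to 0.7. They do not say how many outpatients will have a PCR comparison; 1500 is assumed, as is 90% agreement. If a fraction f of people give two tests and the rest one, the design effect is DE = 1 + ICC × 2f/(1+f), and the interval should be about √DE times as wide.
- f = 1: DE = 1.5, √DE = 1.22. With n = 3000 tests the plain limits are 88.9–91.0%; on 3000/1.5 = 2000 they are 88.6–91.2%.
- f = 0.25: DE = 1.2, √DE = 1.095. With n = 1875 the limits move from 88.6–91.3% to 88.4–91.4%.
- Actual coverage of the plain 95% interval is about 2Φ(1.96/√DE) − 1, which is 89% for f = 1 and 93% for f = 0.25. Beta-binomial simulation agrees within about a point. Over ICC 0.1 to 0.7 with f = 1, coverage runs from 94% to 87%.
- One test per person: DE = 1, no effect.

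With fewer people compared, the limits widen, but the relative correction √DE stays the same.

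**4. Five hospitalised days pooled per test (not an analysis in the plan).** DE = 1 + 4 × ICC = 3 at ICC 0.5.
- 15 patients, 75 tests, 80% agreement: plain 69.5–87.6%. On 75/3 = 25 effective tests it is 60.4–91.6% with a normal quantile, or 58.3–92.3% with a t quantile on 14 df.
- 60 patients, 300 tests: plain 75.1–84.2%; on 100 effective tests 71.0–86.7%.
- Simulated coverage of the plain interval at ICC 0.5: 72% (15 patients) and 74% (60) at 80% agreement; 78% and 76% at 85%.

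**5. Does the remedy work?** Agresti-Coull was simulated on n/DE, with DE estimated from the participant-clustered variance, at ICC 0.5, five tests each, and 80/85/90% agreement.
- 60 patients: about 95% throughout.
- 15 patients: 95/95/94% with a t quantile, against 93/93/90% with a normal quantile. A percentile cluster bootstrap gave 92% at 80% agreement and 84% at 90%.
- When no disagreement is observed, DE cannot be estimated. The 94% requires DE to be set then to the number of tests per patient (5). If it is set to 1, coverage falls to about 91%.

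**The case against.** The case for leaving the text alone is reasonable. Recruitment states a ceiling, the total moves by only 1.5%, and no aim, outcome or feasibility threshold uses the hospitalised set. The outpatient limits shift by about 0.3 percentage points at most in the example above. The 80% and 85% criteria are rules on point estimates, and neither analysis section attaches an interval to a decision. The usability cohort gives one test each. The 24-hour window, in Analysis of the Validity Outcomes and again in Data Acquired, leaves few people with two PCR-paired tests: two qualify only if the swab falls close to both.

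Most of this stands for the companion point, which is why it is minor. It does not remove the contradiction in the hospitalised number. The Study Design Summary gives 3060 without a ceiling, and Study Population gives 15 for the same group.

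A reader might go further and infer three things that the documents do not support:
- *That the planned intervals have coverage near 72–78%.* That needs per-test pooling of the five hospitalised days, which the plan neither states nor excludes, together with an assumed ICC.
- *That the sensitivity and specificity intervals are seriously too narrow.* The 24-hour rule usually leaves one test per person.
- *That inpatient samples have no defined analysis.* Percent agreement against saliva direct PCR is defined for them. Only the five-day concordance with the CLIA test lacks a formula and unit.

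**Conclusion.** The hospitalised sample size is wrong as written. It is 15 in Study Population and 60 in Recruitment, and only 60 fits the stated total of 3060. This rests on addition alone. The documents do not say which figure is intended. The consequence is about a twofold difference in the width of any hospitalised proportion.

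The interval point is real but minor. For the written outpatient analyses the interval is at most about 22% too narrow on the width scale at an assumed ICC of 0.5, with everyone giving two tests. It is about 10% if a quarter do, and nil with one test each. No feasibility threshold is affected. The missing unit for the five-day hospitalised concordance is a missing detail, not a threat to a stated conclusion. It is worth closing because per-test pooling is the one route by which repeat testing would matter much.

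**What to change.** 1. **Reconcile** the Study Design Summary, Study Population and Recruitment to one hospitalised number and one total.
2. **Add to General Considerations:** where a participant contributes more than one test to a proportion, the 95% interval is Agresti-Coull on n divided by the design effect. The design effect is the participant-clustered variance over p(1−p)/n, not below 1, and set to the number of tests per participant if no disagreement, or no agreement, is observed. A t quantile on participants minus 1 is used. Where outpatient data are multiply imputed, the proportion and clustered variance are computed in each imputed data set and combined by Rubin's rules. The alternative is to analyse one prespecified test per participant, which keeps the plain interval. Choose one in advance.
3. **Define the hospitalised concordance by study day**, one test per patient per day, showing the number of paired CLIA results each day. Any pooled five-day figure follows item 2. State whether a complete case is a patient-day or a patient with all five days.

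**Cost.** Wording and one reconciled number, with no new data. Intervals widen where tests repeat: about 22% with two tests each at ICC 0.5, and at most about 41% (√2) at ICC 1. A pooled figure for 15 patients would be about 34 points wide instead of 18. By-day intervals with 15 patients are about 40 points wide. Using one test per participant discards some data.

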**Analysis Sets:**

There are two key analysis sets that are subsets of the study population. The first subset consists of outpatients. The second subset consists of the patients hospitalized for COVID-related complications who will be tested daily for 5 days.

**Analysis of the Feasibility Outcomes**

Analyses of all feasibility outcomes will be performed in the outpatient analysis set.

The concordance of the test results will be compared to the results of PCR testing. We will calculate the proportion in agreement (# of tests where SnapDx and PCR testing agree/# total tests), the proportion correctly identified as positive (# of tests SnapDx-positive/# PCR-positive), and the proportion correctly identified as negative (# of tests SnapDx-negative/# PCR-negative). A threshold of 80% overall agreement and 85% agreement in the positive tests will indicate the home test is feasible.

Percent confidence in interpretation of the results and that instructions were followed correctly will be summarized as 1) percent of respondents stating that they are at least 80% confident in their interpretation and 2) median and interquartile range of reported confidence levels. Results will be reported separately for participants and technicians.

The proportion of participants who call technical support will be presented and the frequency of the reason for the call will be presented. The proportion of tests that have a sufficient amount of saliva to reach the indicator line will be presented.

The feasibility outcomes will be presented separately by demographic characteristics in a subgroup. For example, we will evaluate whether the concordance is comparable across different age groups, between men and women, etc.

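### The printed formula for positive agreement counts false positives as correct, so the 85% feasibility mark can be met by a test whose true positive agreement is below 85%

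*Combined protocol and SAP*

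**What the plan says.** Analysis of the Feasibility Outcomes defines three measures against PCR:

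- Overall agreement: "the proportion in agreement (# of tests where SnapDx and PCR testing agree/# total tests".
- Positive: "the proportion correctly identified as positive (# of tests SnapDx-positive/# PCR-positive".
- Negative: "the proportion correctly identified as negative (# of tests SnapDx-negative/# PCR-negative".

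The decision rule follows: "A threshold of 80% overall agreement and 85% agreement in the positive tests will indicate the home test is feasible". The same section plans subgroup comparisons, in which "we will evaluate whether the concordance is comparable across different age groups, between men and women, etc".

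Three other places bear on the point:

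- The Validity section under Study Design names agreement measures without formulas: "SnapDx test results will be compared against saliva direct PCR results to determine the positive percent agreement (PPA) and negative percent agreement (NPA".
- General Considerations sets the interval method: "We will use the Agresti-Coull method".
- Analysis of the Validity Outcomes states "The sensitivity, specificity, positive predictive value (PPV), and negative predictive value (NPV) of the test will be estimated using the results collected in outpatients", with neither formulas nor a pass mark.

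**The concern.** The overall measure writes out the condition that the two tests agree. The positive and negative measures do not: each divides a SnapDx total by a PCR total. A test that is SnapDx-positive and PCR-negative therefore adds to the share labelled as correctly identified positives, and false positives can make up for missed infections.

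The label and the formula give different numbers whenever FP > 0, and the rule does not say which governs. The positive measure carries one of the only two numeric marks for declaring the home test feasible, so the choice can decide pass or fail. The negative measure has the same fault but carries no threshold. The 80% mark uses overall agreement, which is correctly defined.

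**Working it through.** **Inputs.** From the plan: the three formulas, the 80% and 85% marks, the Agresti-Coull 95% interval, and 1500 + 1500 = 3000 outpatients (Study Population). Not in the plan, so assumed over a range: PCR-positive share p, sensitivity s (equal to true PPA) and specificity sp. The plan derives no figure from this rule, so there is none to reproduce first.

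**Step 1: size of the error.**

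- Printed positive ratio = (TP+FP)/(TP+FN) = s + (1−sp)(1−p)/p
- Overall agreement = s·p + sp·(1−p)

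The excess over true PPA is (1−sp)(1−p)/p. It is zero only when there are no false positives, and it is never negative.

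**Step 2: lowest true PPA that meets both marks at a fixed specificity.** Minimum s = 0.85 − (1−sp)(1−p)/p. For example, at p=20% and sp=95%: 0.85 − 0.05×0.80/0.20 = 0.65.

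| p | sp 95%: minimum PPA (overall agreement) | sp 98%: minimum PPA (overall agreement) |
|---|---|---|
| 50% | 80% (87.5%) | 83% (90.5%) |
| 30% | 73% (88.5%) | 80% (92.7%) |
| 20% | 65% (89.0%) | 77% (93.8%) |

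The 80% overall mark is met in every cell, so it does not protect against the error.

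**Step 3: lowest true PPA at any specificity.** Let f = FP/PCR-positives. The two marks require s + f ≥ 0.85 and (1−s) + f ≤ 0.20/p. Eliminating f gives s ≥ (1.85 − 0.20/p)/2:

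- p=50%: 72.5%, reached at specificity 87.5%
- p=30%: 59%, at 88.9%
- p=20%: 42.5%, at 89.4%

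The bound reaches 0% only if p ≤ 0.20/1.85 = 10.8% and false positives are at least 85% of the PCR-positive count.

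**Step 4: worked counts.** Take 3000 tests, one per outpatient, with p=20% assumed: 600 PCR-positive and 2400 PCR-negative. Let TP=390, FN=210, FP=120, TN=2280.

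- Printed positive measure: (390+120)/600 = 85.0%, meets the mark
- Overall agreement: (390+2280)/3000 = 89.0%, meets the mark
- True PPA: 390/600 = 65.0% (Agresti-Coull 95% CI 61.1–68.7%), fails
- Printed negative measure: (2280+210)/2400 = 103.8%

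**Step 5: chance of passing.** Simulated with TP and FP binomial, PCR-positives fixed at N·p, and at least 200,000 replicates per case:

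| p, s, sp | N=3000: printed vs correct | N=120: printed vs correct |
|---|---|---|
| 20%, 70%, 95% | 98% vs 0% | 64% vs 4% |
| 30%, 75%, 95% | 83% vs 0% | 59% vs 8% |
| 50%, 80%, 93% | 95% vs 0% | 68% vs 21% |

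N=120 is the size of the usability cohort.

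**Step 6: side effects.** The two printed numerators sum to the total number of tests, and so do the two denominators. One ratio must therefore exceed 100% unless FP = FN. For 2490/2400 the Agresti-Coull centre is (2490 + 1.92)/(2400 + 3.84) = 1.037, so centre × (1 − centre) is negative and the interval cannot be computed.

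The printed positive ratio also moves with p. At a constant 80% sensitivity and 95% specificity it is 85% at p=50%, 92% at 30%, 100% at 20% and 125% at 10%. Subgroups with equal accuracy but different PCR-positive shares would appear to differ.

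**The case against.** The strongest reply is that the formula is shorthand. The label, and the word agreement in the decision rule, both point to TP over PCR-positives, and a false positive is neither correct nor in agreement. That reading is probably what was meant. But the plan does not say so, and a prespecified pass rule should not depend on inferring intent.

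Other points limit the reach:

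- The declared primary feasibility outcome is participant-versus-technician discrepancy, not agreement with PCR. This is true, but the only numeric feasibility rule is still the one against PCR.
- Sensitivity is estimated separately under the validity analysis, which would show the true value. That analysis has no pass mark and is limited to pairs taken within 24 hours.
- A ratio above 100% would alert an analyst. In the worked case, however, the ratio carrying the threshold is a plausible 85.0%; only the negative ratio, which has no threshold, exceeds 100%.
- The feasibility section does not use the terms PPA and NPA, so its formulas need not govern the comparison in the Validity section. This is correct. That section simply has no formula of its own.
- The size depends on the assumptions. At p=50% and 98% specificity the shift is 2 points (83% against 85%), and a test with 80% sensitivity then passes as printed about 0.3% of the time at N=3000. The study enriches for positives, so a high p is plausible. The contrast in pass probability also shrinks at N=120.
- Overall agreement varies with p too (87.5% at p=50% and 93.5% at p=10%, for 80% sensitivity and 95% specificity), so correcting the formula removes only part of the subgroup problem.

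These points bear on size and reach. They do not change the direction of the error or the need to correct it.

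**Conclusion.** The concern holds. The formula contradicts its own label, and the 85% mark rests on the measure so defined. Applied as printed, the rule can pass a test whose true PPA is well below 85%: down to 65–80% at 95% specificity and 77–83% at 98%, for p from 20% to 50%. These figures rest on assumed p and specificity, and the pass probabilities also on the number of paired tests, none of which the plan fixes. The direction needs no assumption, because false positives can only raise the printed ratio. If the formula was shorthand, the defect is one of wording; if it is programmed as written, it can change the feasibility conclusion. It should be corrected before analysis.

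**What to change.** In Analysis of the Feasibility Outcomes, define:

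- PPA = number of tests positive on both SnapDx and PCR / number PCR-positive
- NPA = number of tests negative on both SnapDx and PCR / number PCR-negative

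State that the 85% mark applies to this PPA. Use the same definitions for PPA and NPA in the Validity section and in the subgroup tables.

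The cost is a line of SAP wording, with no change to design, sample size or data collection. Reported agreement will be equal to or lower than under the printed formulas, and a test that would have passed only because of false positives will no longer pass.
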